# **STUDY INFORMATION**

Title	Vfend Special Investigation
	—For prophylaxis of invasive fungal infections in pediatric and adults—
Protocol number	A1501106
Protocol version identifier	Ver. 1.0
Date of last version of protocol	N/A
Active substance	Voriconazole
Medicinal product	Vfend 200 mg for Intravenous Use Vfend Tablets 50 mg Vfend Tablets 200 mg Vfend Dry Syrup 2800 mg
Research question and objectives	This study is intended to assess the following items, etc. for the safety and effectiveness of Vfend 200 mg for Intravenous Use, Vfend Tablets 50 mg, Vfend Tablets 200 mg, and Vfend Dry Syrup 2800 mg (hereinafter referred to as product) in daily clinical practice for prophylactic administration of this product for invasive fungal infections in children and adults and review the necessity for further special investigation and post-marketing clinical study.  - Unknown adverse reactions including those associated with long-term use  - Occurrence of adverse reactions under actual clinical settings including long-term use.  - Factors considered to affect the safety and effectiveness of this product
Author	Post-marketing Study Strategy and Management PMS Planning and Operation Group 1
	PPD

# TABLE OF CONTENTS 1. LIST OF ABBREVIATIONS......4 3. AMENDMENTS AND UPDATES......6 6. RESEARCH QUESTION AND OBJECTIVES ......7 7. RESEARCH METHODS .......7 7.3.6. Effectiveness evaluation 13 7.6. Data management 16

7.6.1. Data collection method	16
7.6.2. Patient registration	16

# 1. LIST OF ABBREVIATIONS

Acronym	Tittle
AE	adverse event
Al-P	Alkaline phosphatase
ALT	Alanine aminotransferase
AST	Aspartate aminotransferase
BUN	Blood urea nitrogen
CRP	C-reactive protein
EDP	exposure during pregnancy
GGT	Gamma-glutamyltransferase
IEC	Independent Ethics Committee
IRB	institutional review board
NIS	Non interventional study
SRSD	Single Reference Safety Document

#### 3. AMENDMENTS AND UPDATES

N/A

#### 4. MILESTONES

Milestone	Planned date	
Start of data collection	October 2015	
End of data collection	October 2018	
Final study report	To be decided	

#### 5. RATIONALE AND BACKGROUND

Vfend (nonproprietary name: voriconazole) is a new triazole therapeutic agent for invasive fungal infections developed by Pfizer UK Central Laboratory which has a similar structure as fluconazole.

Vfend selectively acts on fungal cells and demonstrates its antimycotic action by inhibiting cytochrome P450-dependent  $14\alpha$ -demethylase in the ergosterol biosynthesis which is a component of fungal cell membranes.

Vfend 200 mg for Intravenous Use, Vfend Tablets 50 mg, and Vfend Tablets 200 mg were approved as drugs indicated for invasive aspergillosis, pulmonary aspergilloma, chronic necrotic pulmonary aspergillosis, candidemia, esophageal candidiasis\*, candidal peritonitis, bronchopulmonary candidiasis, cryptococcal meningitis, pulmonary cryptococcosis, fusariosis, and scedosporiosis on April 11, 2005.

Furthermore, since the options for antimycotic agents which can be used for pediatric patients are limited in Japan, the "Review Committee on Unapproved or Off-Labeled Drugs with High Medical Need" held in April 2010 evaluated that the pediatric indication of voriconazole had high medical need and requested the development of voriconazole for pediatric use. The pharmacokinetic study of voriconazole in pediatric patients was conducted in Japan and the pediatric indication of voriconazole was approved on September 26, 2014. In so doing, since the dosage and administration in children need to be adjusted per weight and the use of tablets in younger children is expected to be difficult, the approval of oral dry syrup was also obtained as a new dosage form.

While the prophylactic administration of antifungal agents for patients with hematopoietic stem cell transplantation is recommended in the domestic and overseas guidelines, considering the fact that the prophylactic administration of voriconazole is recommended especially for invasive aspergillosis as one of the options, etc., the application for additional indication for prophylaxis of deep mycosis in patients with hematopoietic stem cell transplantation was submitted and the approval was obtained on August 24, 2015.

The Special Investigation of Vfend - For prophylaxis of invasive fungal infections in children and adults - (hereinafter referred to as "This study") will be conducted to collect information on occurrence of adverse reactions by Vfend 200 mg for Intravenous Use, Vfend Tablets 50 mg, Vfend Tablets 200 mg, and Vfend Dry Syrup 2800 mg by type of diseases, etc., quality, effectiveness and safety in daily clinical practice for prophylactic administration of this product for invasive fungal infections in children and adults. The information collected from this study shall be used to provide proper use information and prepare documents for the application of re-examination.

This study shall be conducted in strict compliance with the "Ordinance concerning Standards for Conducting Post-Marketing Study and Studies on Pharmaceutical products" (MHLW Ordinance No. 171 dated December 20, 2004)

Data obtained from the patients registered in this study will be reported to the MHLW pursuant to the Pharmaceutical and Medical Device Act; pertinent to which, data may be publicly posted in MHLW's "Pharmaceutical and Medical Device Safety Information" and "Pharmaceuticals and Medical Devices Information Website (http://www.info.pmda.go.jp) as a listing of patients, which will present the names of drugs, adverse reactions, sex, age (increment of 10 years), and other relevant information. Furthermore, data collected may also be disclosed if the MHLW is required to disclose such information in accordance with the "Act on Access to Information Held by Administrative Organs" (Law No. 42 dated May 14, 1999) provided that in no event will the names of physicians, medical institutions, and other personal information be subject to such disclosure, nor will it be posted or disclosed in any form or shape.

\*Only for tablets and dry syrup

#### 6. RESEARCH QUESTION AND OBJECTIVES

This study is intended to assess the following items, etc. for the safety and effectiveness of Vfend 200 mg for Intravenous Use, Vfend Tablets 50 mg, Vfend Tablets 200 mg, and Vfend Dry Syrup 2800 mg (hereinafter referred to as product) in daily clinical practice for prophylactic administration of this product for invasive fungal infections in children and adults and review the necessity for further special investigation and post-marketing clinical study.

- Unknown adverse reactions including those associated with long-term use
- Occurrence of adverse reactions under actual clinical settings including long-time use
- Factors considered to affect the safety and effectiveness of this product

### 6.1. Safety Specifications

[Important identified risks] Hepatic toxicity, QT prolongation, ventricular tachycardia, ventricular fibrillation, arrhythmia, atrioventricular block complete, visual events, phototoxicity, peripheral neuropathy such as Guillain-Barre syndrome, renal failure, blood disorder, interstitial pneumonia, heart failure, consciousness disturbed

[Important potential risks] None

[Important missing information] Safety of pediatric use

#### 7. RESEARCH METHODS

# 7.1. Study design

This study is a prospective multicenter cohort study conducted in patients receiving the product; for which, case report forms will be recorded based on data presented in medical records obtained from daily clinical practice.

# 7.2. Setting

Patients who were administered this product for the purpose of prophylaxis of invasive fungal infections at the initiation of administration of this product

# 7.2.1. Inclusion criteria

- 1. Patients who have not developed invasive fungal infections at the time of initiation of administration of this product (patients with medical history of invasive fungal infections can be registered)
- 2. Patients with history of hematopoietic stem cell transplantation or patients who plan to receive hematopoietic stem cell transplantation

The indications and dosage and administration of this product are as follows. The latest package insert should be referred to when administering this product.

# [ INDICATIONS]

Severe mycosis as follows:

- Invasive Aspergillosis, Pulmonary aspergilloma, Chronic necrotic pulmonary aspergillosis.
- Candidemea, Esophageal Candidasis\*, Candidal peritonitis, Bronchopulmonary candidiasis.
- Cryptococcal meningitis, Pulmonary Cryptococcosis.
- Fusariosis.
- Scedosporiosis.

\* Only for tablets and dry syrup

Prophylaxis of invasive fungal infections in patients undergoing HSCT (Hematopoietic Stem Cell Transplantation)

# [ DOSAGE AND ADMINISTRATION ]

<for Intravenous Use>

Adult	Voriconazole is administered by intravenous drip infusion at the dose of 6 mg/kg twice daily on day 1 and 3 mg/kg or 4 mg/kg twice daily from day 2 onward.
Children (Aged 2 to <12 and 12 ≥ whose body weight is less than 50 kg)	9 mg/kg as voriconazole twice daily on day 1 and 8 mg/kg twice daily from day 2 should be given intravenously. Dose may be increased depending on condition of patients or if poorly responded_by 1 mg/kg at a time, and dose in intolerant patients should be reduced by 1 mg/kg at a time.
Children (Aged ≥12 whose body	6 mg/kg as voriconazole twice daily on day 1 and 4 mg/kg twice
weight is 50 kg or more)	daily from day 2 should be given intravenously.

<tablet></tablet>	
Adult (body weight ≥40 kg)	A recommended oral dose of voriconazole is 300 mg twice daily between meals on day 1, and 150 or 200 mg/dose twice daily between meals on day 2 and thereafter. Dose may be increased depending on condition of the patients or if poorly responded; provided that a total daily dosage should not exceed 400 mg/dose twice daily on day 1 and 300 mg/dose twice daily on day 2 and thereafter.
Adult (body weight <40 kg)	A recommended oral dose of voriconazole is 150 mg twice daily between meals on day 1, and 100 mg/dose twice daily between meals on day 2 and thereafter. Dose may be increased from day 2 onward depending on condition of patients or if poorly responded; provided that a total daily dosage should not exceed 150 mg/dose twice daily.
Children (Aged 2 to <12 and ≥12 whose body weight is less than 50 kg)	After the administration of Voriconazole injection, a recommended maintenance oral dose of voriconazole following injection therapy is 9 mg/kg/dose twice daily between meals. Dose may be increased by 1 mg/kg at a time depending on condition of patients or if poorly responded, and dose in intolerant patients should be reduced by 1 mg/kg at a time (unless the dosage was at its maximum 350 mg, in which case, dose should be reduced by 50 mg at a time). A total daily dosage should not exceed 350 mg/dose twice daily.
Children (Aged ≥12 whose body weight is 50 kg or more)	After the administration of Voriconazole injection, a recommended maintenance oral dose of voriconazole following injection therapy is 200 mg/dose twice daily between meals; which may be increased up to 300 mg/dose twice daily depending on condition of patients or if poorly responded.
<dry syrup=""></dry>	
Adult (body weight ≥40 kg)	A recommended oral dose of voriconazole is 300 mg twice daily between meals on day 1, and 150 or 200 mg/dose twice daily between meals on day 2 and thereafter. Dose may be increased depending on condition of patients or if poorly responded; provided that a total daily dosage should not exceed 400 mg/dose twice daily on day 1 and 300 mg/dose twice daily on day 2 and thereafter.
Adult (body weight <40 kg)	A recommended oral dose of voriconazole is 150 mg twice daily between meals on day 1, and 100 mg/dose twice daily between meals on day 2 and thereafter. Dose may be increased from day 2 onward depending on condition of patients or if poorly responded; provided that a total daily dosage should not exceed 150 mg/dose twice daily.
Children (Aged 2 to <12 and ≥12 whose body weight is less than 50 kg)	After the administration of Voriconazole injection, a recommended maintenance oral dose of voriconazole following injection therapy is 9 mg/kg/dose twice daily between meals. Dose may be increased by 1 mg/kg at a time depending on

Children (Aged ≥ 12 whose body weight is 50 kg or more)	condition of patients or if poorly responded, and dose in intolerant patients should be reduced by 1 mg/kg at a time (unless the dosage was at its maximum 350 mg, in which case, dose should be reduced by 50 mg at a time).  A total daily dosage should not exceed 350 mg/dose twice daily.  After the administration of Voriconazole injection, a recommended maintenance oral dose of voriconazole following injection therapy is 200 mg/dose twice daily between meals;
	injection therapy is 200 mg/dose twice daily between meals; which may be increased up to 300 mg/dose twice daily depending on condition of patients or if poorly responded.

#### 7.2.2. Exclusion criteria

Patients who correspond to the following must not be registered to this study.

- Patients who have been registered to this study before

#### 7.2.3. Sites for this study

Sites with presence of doctors specialized in the target therapeutic area primarily in the following departments, at which, the product can be prescribed:

Departments of hematology, pediatrics, pediatric hematology, etc.

# 7.2.4. Planned investigation period

Investigation period: October 2015 to October 2018

Registration period: October 2015 to August 2018

(Registration will be discontinued even before the end of the registration period if the target number of patients is reached)

#### 7.2.5. Study procedure

#### 7.2.5.1. Study methods

This study will be conducted with a central registration system.

# 7.2.6. Observation period

The observation period shall start on the day the administration of this product begins and ends on the day the administration is completed; provided that the patients will be followed until the last day of the investigation period as long as possible if the administration period prolongs.

#### 7.3. Variables

This study will be conducted in accordance with the following assessment schedule.

Table 1. Schedule of observation

_	Table 1. Selle	edule of obser	vation	
	Timing Variables	Baseline	Observation period	Termination of observation period
	ID number	•		
	Sex	•		
Age at the time when the administration of the targeted drug is initiated		•		
Вас	Height/body weight	•		
Background	Hospitalization status (inpatient/outpatient)	•		
nd	Objective of administration	•		
	History of hematopoietic stem cell transplantation	•		
	Disease history	•		
	Prior antifungal agents administered for prophylaxis of invasive fungal infections	•		
Pres	ence/absence of pregnancy		•	•
	eted drug use record	•		
Concomitant medications, concomitant medications for careful administration/contraindication, and immunosuppressants for prophylaxis of invasive fungal infections			•	
Tests			•	
Effectiveness evaluation				•
Completion (discontinuation) record				•
Confirmation of presence/absence of adverse events that correspond to major investigation items (presence/absence of occurrence of hepatic toxicity/visual events)			•	
Adverse events			•	

• : Data items

# 7.3.1. Background

Input the information at the initiation of this product

- (1) ID number
- (2) Sex
- (3) Age (at the time when the administration of the targeted drug is initiated)
- (4) Height
- (5) Body weight
- (6) Hospitalization status (inpatient/outpatient)
  (7) Objective of administration (infection for which this product is prescribed)
  -Primary prophylaxis\* / secondary prophylaxis\*\* / others
- \*Primary prophylaxis: Prophylaxis of patients without history of fungal infection

- \*\*Secondary prophylaxis: Prophylaxis of patients with history of fungal infection
- (8) History of hematopoietic stem cell transplantation (before initiation of administration or immediately after initiation of this product)
- Date of hematopoietic stem cell transplantation, type of transplantation (autograft, allogeneic full transplantation/allogeneic mini-transplantation), source of transplantation (bone marrow/cord blood/peripheral stem cell)
- Occurence of GVHD (graft versus host disease)
- Disease indicated for transplantation/severity
- (9) Presence/absence and severity of hepatic function disorder, renal impairment
- (10) Disease history (medical history and complications)
- Name of disease or syndrome, as well as history or pre-existing disease
- (11) Antifungal agents administered from the date of hematopoietic stem cell transplantation to the day before the start date of administration for prophylaxis of invasive fungal infections (name of antifungal agent, route of administration, reason for discontinuation)

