5.4. Subgroup Analysis

Subgroup analyses of safety and effectiveness will be performed for the following patient background factors and other factors. Levels in parentheses are levels of subgroups, and underlined levels are the reference for calculation of risk ratio and risk difference.

- Sex [male, female]
- Age (1) [<15 years, ≥ 15 years]
- Age (2) [<65 years, ≥65 years)
- Age (children 1) [newborns (<1 month after birth), infants (≥1 month to <1 year), younger children (≥1 to <7 years), children (≥7 to <15 years)]
- Age (children 2) [<2 years, ≥ 2 to <15 years]
- Hospitalized Status [inpatient, outpatient]
- Objective of treatment [primary prophylaxis (patients without history of fungal infection), secondary prophylaxis (patients with history of fungal infection), others]
- Type of transplantation [autograft, allogeneic full transplantation, allogeneic mini-transplantation]
- Source of transplantation [bone marrow, cord blood, peripheral stem cell]
- Occurrence of GVHD (graft versus host disease) [absent, present]
- Indication for transplantation¹ [leukemia, myelodysplastic syndrome, malignant lymphoma, myeloma, others]
- Severity of indication for transplantation [mild, moderate, severe]
- Hepatic dysfunction [absent, present]
- Severity of hepatic dysfunction [mild, moderate, severe]
- Renal dysfunction [absent, present]
- Severity of renal dysfunction [mild, moderate, severe]
- Past medical history [absent, present]
- Concurrent illness [absent, present]
- Congenital severe immunodeficiency² [absent, present]
- White blood cell count before administration [$<3000/\mu$ L, $\geq 3000/\mu$ L]
- Neutrophil count before administration [$<500/\mu$ L, $\geq 500/\mu$ L]
- Concomitant use of broad-spectrum antibiotics [absent, present]
- Use of contraindicated concomitant medications [absent, present]
- Use of concomitant medications requiring precautions for coadministration [absent, present]
- Concomitant use of immunosuppressants (other than steroids) [absent, present]
- Concomitant use of steroids [absent, present]
- Concomitant use of steroids or immunosuppressants other than steroids [absent, present]
- Concomitant use of other antifungal agents [absent, present]
- Prior treatment (antifungal agents administered for prophylaxis of invasive fungal infections)
 [absent, present]
- Long-term treatment [$\leq 180 \text{ days}$, $\geq 180 \text{ days}$]

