8.2.4.4. Subgroup Analysis

To evaluate the relationship between patient background factors and effectiveness, subgroup analyses of the proportion of patients who developed invasive fungal infections and the proportion of patients with successful prophylaxis of invasive fungal infections will be performed in accordance with Section 8.1.3 for each of the factors specified in Section 5.4. Risk ratio and risk difference will not be calculated for concomitant use of steroids or immunosuppressants other than steroids.

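### The GVHD subgroup factor has no defined time window or at-risk population, so its risk ratio mixes GVHD with transplant type and timing of start, with bias in an unknown direction (minor)

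*Protocol*

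**What the plan says.** Protocol 7.3.1 opens the background items with the instruction "Input the information at the initiation of this product". Item (8) there is the transplant history, qualified as "before initiation of administration or immediately after initiation of this product"; the length of *immediately after* is not given. The item includes the transplant date, type and source, and "Occurence of GVHD (graft versus host disease". No onset date is requested for GVHD.

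In Table 1 (Protocol 7.3) the row "History of hematopoietic stem cell transplantation" is marked at baseline only, and GVHD has no row of its own.

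Inclusion criterion 2 (Protocol 7.2.1) also admits "patients who plan to receive hematopoietic stem cell transplantation". Autograft patients are in scope, since SAP 5.4 lists "Type of transplantation [autograft, allogeneic full transplantation, allogeneic mini-transplantation" as levels of a factor.

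SAP 5.4 defines the factor as "Occurrence of GVHD (graft versus host disease) [absent, present", without a time point, a restriction to allogeneic recipients, or a level for patients not at risk. SAP 8.2.4.4 states that the effectiveness comparisons "will be performed in accordance with Section 8.1.3 for each of the factors specified in Section 5.4"; SAP 8.2.3.4 does the same for adverse drug reactions. SAP 8.1.3 supplies unadjusted risk ratios and risk differences. Under SAP 8.2.3.5 and 8.2.4.5, a ratio of at least 2 or at most 0.5 leads to further tabulation or listing.

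**The concern.** Taking GVHD as a complication of donor grafts, a patient can be classified by GVHD status at the start only if an allogeneic transplant has already taken place. As planned, *absent* can contain four kinds of patient:

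- allogeneic recipients without GVHD;
- allogeneic recipients whose GVHD begins after the start;
- patients not yet transplanted;
- autograft patients, who are never at risk.

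*Present* is largely confined to allogeneic recipients who were transplanted and already had GVHD around the start. The comparison is then partly allogeneic against autologous, and partly late against early start of prophylaxis.

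Factors that affect safety and effectiveness are a stated objective (Protocol 6, SAP 2.2), and the ratio decides whether a factor gets a closer look. The protocol treats other time-varying items differently: pregnancy (7.3.1.1) and immunosuppressants (7.3.3.1) are recorded to the end of observation.

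**Working it through.** The documents give no GVHD rate, autograft share, share starting before transplant, or GVHD effect. There is no plan figure to reproduce, and every input below is an assumption.

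**Mixture formula.** Set the outcome risk of allogeneic patients who never have GVHD to 1. Let RR be the true ratio for GVHD, f the share of *absent* with later GVHD, a the autograft share of *absent*, and k the autograft risk relative to 1. Then

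planned ratio = RR / [f·RR + a·k + (1 − a − f)].

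This gives later GVHD the full RR, so it is an upper limit on the pull toward 1. For RR above 1, the planned ratio is below RR when f(RR − 1) > a(1 − k) and above RR when the inequality is reversed.

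**Later GVHD only (a = 0):**

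| True RR | f = 10% | f = 30% | f = 50% |
|---|---|---|---|
| 2 | 2/1.1 = 1.82 | 2/1.3 = 1.54 | 2/1.5 = 1.33 |
| 3 | 3/1.2 = 2.50 | 3/1.6 = 1.88 | 3/2 = 1.50 |

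**Autografts only (f = 0, a = 30%):** true RR 2 becomes 2/0.79 = 2.53 at k = 0.3 and 2/1.15 = 1.74 at k = 1.5. With no GVHD effect at all (RR 1), the ratio is 1/0.79 = 1.27 or 1/1.15 = 0.87.

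**Both (RR 2, f = 10%, a = 30%):**

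- k = 0.3: 2/(0.20 + 0.09 + 0.60) = 2.25
- k = 1: 2/(0.20 + 0.30 + 0.60) = 1.82
- k = 1.5: 2/(0.20 + 0.45 + 0.60) = 1.60

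Here f(RR − 1) = 0.10 and a(1 − k) = 0.30(1 − k), so the direction changes at k = 2/3.

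**Head-count illustration.** Assume 200 patients: 160 allogeneic and 40 autograft. Assume 40% of allogeneic patients ever have GVHD, with outcome risk 10% with it and 4% without (true ratio 2.5). Half of the allogeneic patients start before transplant, and all GVHD in the other half is present at start.

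- *Present*: 80 × 0.40 = 32.
- *Absent*: 48 + 80 (of whom 32 have later GVHD) + 40 autograft = 168.
- Autograft risk 4%: (32 × 0.10 + 136 × 0.04)/168 = 5.14%; ratio 10/5.14 = 1.94.
- Autograft risk 1.2% (0.3 times): (3.2 + 96 × 0.04 + 40 × 0.012)/168 = 4.48%; ratio 2.23.

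With 25% or 75% starting before transplant, the ratios are 2.16 or 1.80 at 4% autograft risk, and 2.57 or 2.02 at 1.2%. The planned ratio can thus fall on either side of the trigger of 2, and even above the true 2.5.

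**What restriction does (50% case).** The contrast becomes 32 against 48 patients, with 3.2 and 1.92 expected events and ratio 2.5. The standard error of the log ratio is √(1/3.2 − 1/32 + 1/1.92 − 1/48) = 0.884, for an approximate 95% interval of 0.44 to 14.1. As planned (32 against 168, 3.2 and 8.64 events, 4% autograft risk) it is 0.57 to 6.6. If only half of the GVHD among these 80 is present at start, restricted *absent* is 64 patients with risk (16 × 0.10 + 48 × 0.04)/64 = 5.5%, and the ratio is 10/5.5 = 1.82.

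**The case against.** A reader might infer that the planned ratio is simply diluted, so that a real GVHD effect would miss the trigger of 2. The documents do not support that. Autograft patients in *absent* are not misclassified; they bring confounding by transplant type, which can raise the ratio. Missing the trigger in the illustration depends on giving autograft patients the same risk as allogeneic patients without GVHD.

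A reader might also infer that every autograft patient and every later GVHD case is certain to be coded *absent*. That too is not settled:

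- The transplant-history window runs past the start by an undefined length, and Protocol 7.6.1 has the form completed after observation ends, so some sites may enter later GVHD.
- SAP 5.4 ties white cell and neutrophil counts to the time before administration, but not GVHD.
- A blank entry becomes *unknown* under SAP 7.
- Later GVHD could be reported as a dated adverse event (Protocol 7.3.7, 9.4.1).

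These points stand, but they confirm that the factor is undefined. Sites may differ, status could be recorded after the outcome, and neither document links adverse event data to the factor.

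The consequence is also limited. GVHD is one of about 30 factors, SAP 4.1 makes the testing exploratory, Protocol 7.9 concedes that confounding may be inadequately handled, transplant type is a separate factor, and further analysis is allowed whatever the ratio. In the illustration, sampling error far exceeds the shift from 2.5 to 1.94. This limits the severity, but it does not give the factor a meaning.

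**Conclusion.** The point holds as a matter of definition. GVHD status has no stated time window and no at-risk population, and its unadjusted risk ratio and risk difference are confounded by transplant type and timing of start. Neither the size nor the net direction of the bias can be determined from the documents. For a true ratio of 2, the combined scenarios above give 1.60 to 2.25; these rest wholly on assumed shares and risks and show only that both directions are plausible. A claim of net dilution, or that the trigger would be missed, goes beyond the evidence. Severity is minor because the analysis is exploratory; the change is worth making because it is specific and uses items already collected.

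**What to change.** In SAP 5.4, 8.2.3.4 and 8.2.4.4:

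- Label the factor *GVHD at start of product*.
- Compute its risk ratio and risk difference only in allogeneic recipients (full or mini) whose transplant date is on or before the first dose.
- Tabulate autograft patients and pre-transplant starters separately as *not at risk at start*, without a ratio.

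Transplant type, transplant date and start date are already collected (Protocol 7.3.1, 7.6.2.1), so only SAP wording changes. That matters because the planned end of data collection, October 2018, precedes SAP version 4.0 of June 2019.

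The cost is fewer patients and a wider interval, as the illustration shows; if a category has 5 patients or fewer, SAP 8.1.3 suppresses the ratio altogether. Restriction does not remove GVHD that begins after the start, which remains in *absent*. The report should therefore read the result as relating to GVHD status at start only, not to GVHD during treatment.

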#### 7.6.2. Patient registration

#### 7.6.2.1. Procedure of patient registration

#### (1) Registration

The following information regarding registration should be recorded in the registration forms if this product is given to patients who meet the following registration criteria; patients should be registered via FAX at the registration center until the target number of patients is registered. Patients should be registered via FAX within 2 weeks from the initiation of administration of this product with the start date of administration as Day 1.

- 1) Registration criteria
- Patients who have not developed invasive fungal infection at the initiation of administration with this product
- Patients who received hematopoietic stem cell transplantation or patients who plan to receive hematopoietic stem cell transplantation
- 2) Registration data

Patient identification number, sex, age at the initiation of administration, date on which administration of this product begins and eligibility to registration criteria

[ Patient Registration Center ]

[contact] (Accessible 24 hours a day)

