8.2.3.4. Subgroup Analysis

The number and proportion of patients who experienced at least one adverse drug reaction will be tabulated for each factor specified in Section 5.4. To evaluate the relationship between patient background factors and the development of adverse drug reactions, the analysis specified in Section 8.1.3 will be performed. Risk ratio and risk difference will not be calculated for concomitant use of steroids or immunosuppressants other than steroids.

The listing of adverse drug reactions will be prepared for contraindicated patients. The number and proportion of patients with adverse drug reactions will be tabulated by SOC and PT as necessary.

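### A patient who starts the product before a first transplant cannot be recorded as having prior antifungal treatment, yet the SAP compares prior treatment absent versus present in all patients without stating the window

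*Protocol*

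**What the plan says.** **Who may enter.** Protocol 7.2.1 accepts patients with a past transplant and also "patients who plan to receive hematopoietic stem cell transplantation". The registration criteria in Protocol 7.6.2.1 repeat this: "Patients who received hematopoietic stem cell transplantation or patients who plan to receive hematopoietic stem cell transplantation". Protocol 7.3.1 item (8) expects both orders of events, since it collects "History of hematopoietic stem cell transplantation (before initiation of administration or immediately after initiation of this product".

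**What is collected.** Protocol 7.3.1 item (11) limits the prior-prophylaxis record to "Antifungal agents administered from the date of hematopoietic stem cell transplantation to the day before the start date of administration". Table 1 in Protocol 7.3 names the same item without any window: "Prior antifungal agents administered for prophylaxis of invasive fungal infections".

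**How it is analysed.** SAP 5.4 lists the factor as "Prior treatment (antifungal agents administered for prophylaxis of invasive fungal infections", with the two levels *absent* and *present*. SAP 8.2.2 repeats it as a background factor. Neither place gives a window, a not-applicable level or a restriction to patients already transplanted.

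The factor then enters two sets of comparisons:

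- Safety, SAP 8.2.3.4: "The number and proportion of patients who experienced at least one adverse drug reaction will be tabulated for each factor specified in Section 5.4", with the risk ratio and risk difference of SAP 8.1.3.
- Effectiveness, SAP 8.2.4.4: "To evaluate the relationship between patient background factors and effectiveness, subgroup analyses of the proportion of patients who developed invasive fungal infections" and of the success proportion, again for every factor in 5.4.

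**The concern.** Item (8) of the background record was written to cover patients who start the product shortly before transplant. Item (11) was not. For those patients the collection window opens after it has closed, and no agent can fall inside it.

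A reader of the SAP label alone would take the factor to mean any earlier antifungal prophylaxis. Two things could then go wrong:

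- Patients who did receive prophylaxis before the product, but started the product before a first transplant, may be counted in the reference group.
- *Present* can arise only in patients with a transplant before first dose. The comparison is therefore partly one of starters after transplant with starters before it. This holds even if no pre-transplant starter had earlier prophylaxis.

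Factors affecting safety and effectiveness are a stated objective (Protocol 6, SAP 2.2), and these subgroup tables are how the SAP pursues it. A risk ratio of at least 2 or at most 0.5 also decides which factors receive further tabulation or listing (SAP 8.2.3.5 and 8.2.4.5).

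**Working it through.** **The window.** It runs from the transplant date T to the day before first dose, S − 1. It contains at least one day only if T ≤ S − 1. A patient starting before a first transplant has S < T, so the window is empty.

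**No figure in the plan to reproduce.** The sample-size figures do not involve this factor. From the documents I take only the planned 200 patients (Protocol 7.5.1). They give no share of pre-transplant starters, no rate of earlier prophylaxis and no risk by timing of start. Everything below is assumed, and assumes further that empty windows are coded *absent*.

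**Illustration 1: misclassification.** Assume 50% prior use among post-transplant starters, and a risk of 40% with and 20% without prior use, so the true risk ratio is 2. Let m be the share of the *absent* group that was truly pretreated. Then

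observed risk ratio = 0.40 / (0.20 + 0.20 × m) = 2 / (1 + m).

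| Start before transplant | Prior use among them | Recorded present | Recorded absent | Misclassified | m | Observed risk ratio |
|---|---|---|---|---|---|---|
| any share | 0% | – | – | 0 | 0 | 2.0 |
| 20% (40) | 20% | 80 | 120 | 8 | 0.067 | 1.88 |
| 40% (80) | 50% | 60 | 140 | 40 | 0.286 | 1.56 |
| 80% (160) | 80% | 20 | 180 | 128 | 0.711 | 1.17 |

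For the third row: 120 post-transplant starters × 0.50 = 60 present; 60 + 80 = 140 absent; 80 × 0.50 = 40 misclassified; 2 / (1 + 40/140) = 1.56.

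**Illustration 2: timing of start.** Assume prior treatment has no effect, 40% of post-transplant starters had it, and risk is 10% in pre-transplant and 20% in post-transplant starters. The *present* group then has risk 0.20.

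- 25% start before transplant: absent = 50 + 90 = 140; risk = (50 × 0.10 + 90 × 0.20)/140 = 0.164; risk ratio = 0.20/0.164 = 1.22.
- 50%: absent = 100 + 60 = 160; risk = (10 + 12)/160 = 0.1375; risk ratio = 1.45.
- 75%: absent = 150 + 30 = 180; risk = (15 + 6)/180 = 0.117; risk ratio = 1.71.

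If risk were instead lower after transplant, the ratio would fall below 1. The direction is an assumption as well.

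**The other coding.** If sites leave the item blank, SAP 7 treats a missing categorical item as unknown. Pre-transplant starters would then drop out of the two-level comparison without explanation. That avoids both distortions, but nothing in the SAP says it is intended. SAP 8.2.2 gives hepatic and renal dysfunction an unknown level and gives prior treatment none.

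**The case against.** The case on the other side has several parts.

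- **Coding.** A reader might infer that everyone who starts before transplant is *absent* by construction. The documents do not support that. They do not say how an empty window is coded, and a blank could become unknown. A patient with an earlier transplant who starts before a further one can have a window that is not empty. What stands is narrower: a starter before a first transplant cannot be *present*.
- **Definition.** A reader might also infer that all such patients are misclassified. Against item (11) as written, a pre-transplant starter truly has no prophylaxis in the window. Misclassification arises only if the factor is read as its SAP label suggests, and only for those who had earlier prophylaxis. The label problem remains, as does comparing with patients who could not have been *present*.
- **Overlap with another record.** Antifungal prophylaxis continuing after the product starts is recorded as concomitant medication (Protocol 7.3.3.1) and forms its own factor in SAP 5.4. That recovers some history, but not agents stopped before the product began.
- **Size.** All magnitudes rest on assumed inputs, and the attenuation can be nil. This is correct.
- **Importance.** This is one unadjusted factor among many. SAP 4.1 treats tests as exploratory, SAP 4.2 sets no decision rule, and SAP 8.2.4.1 and 8.2.4.2 do not name the factor. Protocol 7.9 already admits weak control of confounding. This limits the consequence, but a general caveat does not tell a reader that this factor is tied to transplant timing by its definition.

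**Conclusion.** The point holds in a limited form. A patient starting the product before a first transplant cannot be recorded as previously treated, and the SAP compares the two levels in all patients without saying so. If empty windows are coded *absent*, the reference group contains patients who could not be *present*, some of them possibly pretreated, and the factor is confounded with timing of start relative to transplant.

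The size cannot be derived from the documents. Under the assumed inputs, a true risk ratio of 2 appears as 2.0 at best and about 1.2 at worst. Any attenuation takes it below the threshold of 2 for follow-up tabulation or listing. A null factor shows 1.2 to 1.7 if risk doubles after transplant.

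A reader might infer that the study's main results are biased. They are not: the overall adverse reaction, infection and success proportions and the sample size do not use this factor. Only the exploratory prior-treatment comparison and its associated tables are affected.

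**What to change.** In SAP 5.4, 8.2.2, 8.2.3.4 and 8.2.4.4:

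1. Relabel the factor *prior antifungal prophylaxis between transplantation and start of the product*.
2. Calculate the risk ratio and risk difference only in patients with a recorded transplant date before first dose.
3. Show the other patients in a separate row, *not applicable (started before transplant)*, with counts and proportions only.
4. Add a footnote that prophylaxis which ended before the transplant date was not collected.

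**Cost.** SAP wording and one derived flag. The transplant date (Protocol 7.3.1 item 8) and the start date of the product (Protocol 7.6.2.1) are already collected. Exceptions for a single factor have a precedent: SAP 8.2.3.4 and 8.2.4.4 already withhold the risk ratio and risk difference for the combined steroid and immunosuppressant factor.

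**Downsides.** This subgroup has fewer patients. The restriction also does not recover uncollected history: a post-transplant starter whose prophylaxis stopped before the transplant date is still *absent*, which is why the footnote is needed.
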